**9.3.2.2.3.1. Treatment Guidelines and Dose Modifications for Specific Adverse Events of Necitumumab**

Adverse events of concern, which may or may not be associated with necitumumab therapy, include hypersensitivity/infusion-related reactions, skin reactions, conjunctivitis, electrolyte abnormalities, pneumonia and sepsis, and thromboembolic events.

**9.3.2.2.3.1.1. Hypersensitivity/Infusion-Related Reactions**

Hypersensitivity/infusion-related reactions (IRRs) were reported with necitumumab. The onset of events usually occurred after the first or second administration of necitumumab. Monitor patients during and following the infusion for signs of hypersensitivity and IRRs with resuscitation equipment readily available.

Hypersensitivity/IRRs are defined according to the NCI-CTCAE Version 4.0 definition of allergic reaction / hypersensitivity, as follows:

- Grade 1: transient flushing or rash, drug fever  $<38^{\circ}\text{C}$
- Grade 2: rash, flushing, urticaria, dyspnea, drug fever  $\geq 38^{\circ}\text{C}$
- Grade 3: symptomatic bronchospasm, requiring parenteral medication(s), with or without urticaria; allergy-related edema/angioedema, hypotension
- Grade 4: anaphylaxis (a life-threatening event characterized by the rapid onset [often within minutes] of airway obstruction [bronchospasm, stridor, hoarseness], urticaria, and/or hypotension)

Consistent with usual medical practice, selected parenteral medications may be utilized as detailed below. Additional treatments, chosen according to clinical symptoms and local standards, may be utilized at investigator discretion. [Table JFCU.9.3](#) provides general treatment recommendations for hypersensitivity/IRRs to necitumumab.

Table JFCU.9.3. NCI-CTCAE 4.0 Infusion-Related Reactions

Grade of Reaction	Management Recommendations	
	First Occurrence	Second Occurrence
1	
 
Decrease infusion rate by 50% for the duration of the infusion, and monitor patient for worsening of condition.a
 
For all subsequent infusions, premedicate with diphenhydramine hydrochloride 50 mg I.V. (or equivalent); additional premedication may be administered at the investigator's discretion.
 
	
 
Decrease infusion rate by 50% for the duration of the infusion, and monitor patient for worsening of condition.a
 
Administer dexamethasone 10 mg I.V. (or equivalent).
 
For all subsequent infusions, premedicate with diphenhydramine hydrochloride 50 mg I.V. (or equivalent), acetaminophen 650 mg orally (or equivalent), and dexamethasone 10 mg I.V. (or equivalent); additional premedication may be administered at the investigator's discretion.
 

2	
 
Stop the infusion, and resume the infusion when the infusion reaction has resolved to ≤ Grade 1; decrease infusion rate by 50% when the infusion resumes.a
 
Monitor patient for worsening of condition.
 
If necessary, administer diphenhydramine hydrochloride 50 mg I.V. (or equivalent), acetaminophen 650 mg orally for fever, and oxygen.
 
For all subsequent infusions, premedicate with diphenhydramine hydrochloride 50 mg I.V. (or equivalent); additional premedication may be administered at the investigator's discretion.
 
	
 
Stop the infusion, and resume the infusion when the infusion reaction has resolved to ≤ Grade 1; decrease infusion rate by 50% when the infusion resumes.a
 
Administer dexamethasone 10 mg I.V. (or equivalent).
 
Monitor patient for worsening of condition.
 
If necessary, administer diphenhydramine hydrochloride 50 mg I.V. (or equivalent), acetaminophen 650 mg orally for fever, and oxygen.
 
For all subsequent infusions, premedicate with diphenhydramine hydrochloride 50 mg I.V. (or equivalent), acetaminophen 650 mg orally (or equivalent), and dexamethasone 10 mg I.V. (or equivalent); additional premedication may be administered at the investigator's discretion.
 

3-4	
 
Stop the infusion and disconnect the infusion tubing from the patient.
 
Administer diphenhydramine hydrochloride 50 mg I.V. (or equivalent), dexamethasone 10 mg I.V. (or equivalent), bronchodilators for bronchospasm, epinephrine, and other medications / treatments as medically indicated.
 
Hospital admission may be indicated.
 
Permanently discontinue necitumumab.
 
	N/A

Abbreviations: I.V. = intravenously; N/A = not applicable; NCI-CTCAE = National Cancer Institute-Common Terminology Criteria for Adverse Events.

a Once the infusion rate has been reduced for a Grade 1 or 2 hypersensitivity/infusion-related reaction, it is recommended that the lower infusion rate be utilized for all subsequent infusions. The infusion duration should not exceed 2 hours.

If a patient should have a hypersensitivity/IRR to necitumumab, all attempts should be made to obtain an anti-necitumumab antibody and necitumumab PK blood sample as close to the onset of the event as possible, at the resolution of the event, and 30 days following the event. The procedure for sample collection and handling is described in a separate procedural manual.

#### **9.3.2.2.3.1.2. Skin Reactions**

##### **9.3.2.2.3.1.2.1. Reactive Treatment**

Reactive treatment recommendations for skin reaction, based on the Canadian recommendations presented by Melosky et al. (2009), are summarized in [Table JFCU.9.4](#).

Skin rash (any grade) should be treated, as per [Table JFCU.9.4](#). If a patient experiences a Grade 1 or 2 acne-like rash, necitumumab treatment should continue without dose modification or delay. Dose delays and or modifications for necitumumab are to be considered in case of skin reactions of Grade 3 or that are considered intolerable. If a patient experiences Grade 4 skin reactions, treatment with necitumumab should be permanently discontinued.

Table JFCU.9.4. Managing Skin Reactions

Grade of Reaction	Recommendations for Management
1	
 
Administer topical clindamycin 2% and topical hydrocortisone 1% in lotion base twice daily to affected areas until resolution of reaction.
 
Patients are advised to take appropriate protective measures prior to sun exposure to avoid exacerbation of rash severity.
 

2	
 
Administer topical clindamycin 2% and topical hydrocortisone 1% in lotion base twice daily to affected areas until resolution of reaction.
 
If clinically appropriate in the opinion of the investigator, administer oral minocycline or doxycycline 100 mg twice daily (or equivalent), for a minimum of 4 weeks and continuing for as long as rash is symptomatic.
 
Patients are advised to take appropriate protective measures prior to sun exposure to avoid exacerbation of rash severity.
 

3	
 
Administer topical clindamycin 2% and topical hydrocortisone 1% in lotion base twice daily to affected areas until resolution of reaction.
 
Administer oral minocycline or doxycycline 100 mg twice daily (or equivalent), for a minimum of 4 weeks and continuing for as long as rash is symptomatic.
 
Patients are advised to take appropriate protective measures prior to sun exposure to avoid exacerbation of rash severity.
 
Necitumumab administration will be temporarily withheld until symptoms resolve to Grade <math>\leq 2</math>, but not for longer than a maximum of 6 weeks following Day 1 of the most recent treatment cycle.
 
Following improvement to Grade <math>\leq 2</math>, necitumumab may be readministered, with a dose reduction of 50% (400 mg). This dose may be increased to 75% of the original dose (600 mg) after a minimum of 1 treatment cycle (3 weeks), if symptoms do not recur. If symptoms do not recur for another treatment cycle, the dose may be re-escalated to the full recommended dose (800 mg).
 
If reactions do not resolve to Grade <math>\leq 2</math> after 6 weeks (that is, after withholding 2 consecutive doses of necitumumab), or if reactions recur or become intolerable at 50% of the original dose, necitumumab treatment should be permanently discontinued.
 
Patients who experience Grade 3 skin induration / fibrosis will be immediately discontinued from necitumumab.
 

4	
 
Administer topical clindamycin 2% and topical hydrocortisone 1% in lotion base twice daily to affected areas until resolution of reaction.
 
Administer oral minocycline or doxycycline 100 mg twice daily (or equivalent), for a minimum of 4 weeks and continuing for as long as rash is symptomatic.
 
Patients are advised to take appropriate protective measures prior to sun exposure to avoid exacerbation of rash severity.
 
Necitumumab administration must be immediately and permanently discontinued.
 

If necitumumab therapy is delayed due to acneiform rash, abemaciclib may be administered without interruption in the absence of disease progression.

A dermatology referral may be indicated for skin reactions that do not improve following 1-2 weeks of treatment, reactions that are severely symptomatic (for example, necrosis, blistering, or petechial or purpuric lesions), reactions of NCI-CTCAE Grade  $\geq 3$ , or reactions with an uncharacteristic appearance.

As with all concomitant medications/procedures, any actions taken to ameliorate skin toxicity will be documented in the concomitant medication module of the electronic CRF (eCRF).

#### **9.3.2.2.3.1.3. Conjunctivitis**

For patients with treatment-related conjunctivitis <Grade 3, the investigator is advised to initiate symptomatic treatment and follow up observation of the event. If the severity increases to Grade  $\geq 3$ , or symptoms persists for >10 days after symptomatic treatment, the investigator is advised to refer the patient to an ophthalmologist for further evaluation and treatment.

#### **9.3.2.2.3.1.4. Electrolyte Abnormalities**

Consistent with observations with other EGFR mAbs, hypomagnesemia has been very commonly reported in patients treated with necitumumab in combination with cisplatin -based regimens. Hypomagnesemia is considered a class effect for EGFR mAbs. Monitor patients for hypomagnesemia, hypocalcemia, hypokalemia, and hypophosphatemia prior to each administration of necitumumab and after completion of necitumumab, until within normal limits. Prompt repletion is recommended, as appropriate.

#### **9.3.2.2.3.1.5. Pneumonia and Sepsis**

During the conduct of Study JFCL (JFCL; Phase 2 study to investigate carboplatin and soluble paclitaxel with or without necitumumab in patients with squamous NSCLC), following the non-blinded review of SAE cases that included reports related to pneumonia and sepsis, an imbalance in the number of SAEs, including fatal cases, for the necitumumab group compared with the paclitaxel-carboplatin group was found.

The early occurrence of a number of these cases may have indicated an issue regarding the enrollment of the appropriate patients. The sponsor had therefore provided clarification and reinforcement of the inclusion/exclusion criteria, requesting the investigator's particular attention with regard to infections and conditions predisposing to infections ongoing at the time of enrollment in a protocol amendment. During the further conduct of this trial, only single additional reports were received, notably of cases reporting pneumonia and septic complications with concurrent neutropenia.

The review of the data from the Phase 3 study of necitumumab in combination with gemcitabine and cisplatin (JFCC; SQUIRE) did not show any evidence of an increased risk of serious lung infections associated with necitumumab in this combination.

Special attention should be given to early signs of pulmonary infection. Treatment of any infection should be initiated according to local standards.

#### **9.3.2.2.3.1.6. Thromboembolic Events**

In the Phase 3 study JFCC, there was an increase in venous thromboembolic events (VTEs) and arterial thromboembolic events (ATEs) in the investigational arm (necitumumab in combination with gemcitabine and cisplatin) compared to the active control arm (gemcitabine and cisplatin). The relative risk of VTEs or ATEs was approximately 3-fold higher in patients with a reported history of VTEs or ATEs.

In the Phase 3 study JFCB, an increased rate of serious thromboembolic events, including fatal events, has been observed for the combination of necitumumab with pemetrexed and cisplatin as compared with treatment with pemetrexed and cisplatin alone in patients with nonsquamous NSCLC. Administration of necitumumab in combination with pemetrexed and cisplatin is not recommended.

No safety signal with regard to thromboembolic events, including fatal events, has been identified for necitumumab in completed clinical trials when administered as monotherapy or in combination with mFOLFOX-6 chemotherapy.

Treatment of any thromboembolic events occurring under necitumumab treatment should be as clinically indicated according to local standards, and the continuation of necitumumab therapy in these cases should be decided by the investigator after thorough risk-benefit assessment for the individual patient.

#### **9.3.2.2.3.1.7. Cardiorespiratory Disorders**

An increased frequency of cardiorespiratory arrest or sudden death was observed with necitumumab. Cardiorespiratory arrest or sudden death was reported in the pivotal Study JFCC (SQUIRE) in 2.8% (15/538) of patients treated with necitumumab plus gemcitabine and cisplatin compared to 0.6% (3/541) of patients treated with chemotherapy alone. Twelve of the 15 patients died within 30 days of the last dose of necitumumab and had comorbid conditions, including history of chronic obstructive pulmonary disease (n=7), hypertension (n=5), hypomagnesemia (n=4), and coronary artery disease (n=3). Eleven of the 12 patients had an unwitnessed death.

## **9.4. Blinding**

This is an open-label study.

## **9.5. Concomitant Therapy**

Appropriate documentation of all forms of premedications, supportive care, and concomitant medications must be captured at each visit in the CRF. Concomitant medications and supportive care therapies must also be documented at the time of discontinuation and at the 30-day short-term follow-up visit.

With the exceptions listed in the sections below, no other chemotherapy, experimental medications, other anticancer therapy, immunotherapy, hormonal cancer therapy, radiation, surgery for cancer, or experimental medications will be permitted while patients are on study treatment. Palliative radiotherapy, unless required due to progressive disease, is permitted during the study.

The results from an in vitro human recombinant cytochrome P450 (CYP) phenotyping study indicate that oxidative metabolism of abemaciclib is primarily catalyzed by CYP3A4. However, the extent of oxidative metabolism responsible for the systemic clearance of abemaciclib in humans is presently unknown. Based on these in vitro findings, grapefruit juice as well as inducers (for example, phenytoin or carbamazepine) and strong inhibitors of CYP3A4 should be

substituted or avoided if possible ([Attachment 8](#)). In addition, in vitro studies in primary cultures of human hepatocytes indicate that abemaciclib might inhibit the metabolism of CYP2B6 substrate drugs in vivo in human. Based on this finding, sensitive CYP2B6 substrates such as bupropion and efavirenz should be substituted or avoided if possible ([Attachment 8](#)).

Bisphosphonates or denosumab for bone metastasis are permitted.

### **9.5.1. Supportive Care**

Palliative and supportive care for other disease-related symptoms and for toxicity associated with treatment will be offered to all patients on this trial. Supportive care measures may include but are not limited to antidiarrheal agents, antiemetic agents, opiate and nonopiate analgesic agents, appetite stimulants, and granulocyte and erythroid growth factors. Details of interventions, procedures, or blood products (for example, blood cells, platelets, or fresh frozen plasma transfusions) should be recorded on the eCRF. Please see Section [9.3.2.2.3.1](#) for specific information on the management of necitumumab-related hypersensitivity/infusion-related reactions, skin reactions, conjunctivitis, electrolyte abnormalities, pneumonia and sepsis, and serious thromboembolic events. Guidelines regarding the use of other specific supportive care agents are presented below.

### **9.5.2. Colony-Stimulating Factors and Erythropoiesis-Stimulating Agents**

The use of colony-stimulating factors (CSF) or erythropoiesis-stimulating agents (ESAs) are permitted during investigational therapy at the discretion of the investigator.

Because recommendations on the use of CSFs/ESAs are rapidly evolving, investigators should frequently refer to the local, national, or international standards (for example, European Organisation for Research and Treatment of Cancer, European Society for Medical Oncology, National Comprehensive Cancer Network, American Society of Clinical Oncology, American Society of Hematology, and/or Centers for Medicare and Medicaid Services Web sites) for the latest guidelines.

### **9.5.3. Therapy for Diarrhea**

Diarrhea may influence tolerability of abemaciclib. During therapy with abemaciclib, early treatment with antidiarrheal agents (for example, loperamide) is recommended immediately after the first loose stool and should be continued until loose bowel movements cease for 12 hours. If a patient experiences persistent or recurrent Grade 2 diarrhea that does not resolve within 24 hours to either baseline or at least Grade 1, despite maximal treatment with antidiarrheal agents, then dosing should be suspended (until the toxicity resolves to either baseline or at least Grade 1), and the dose of abemaciclib may be reduced by 1 dose level as outlined in [Table JFCU.9.2](#) at the discretion of the investigator. If the same dose level was resumed and Grade 2 diarrhea recurs despite maximal treatment with antidiarrheal agents, the dose must be reduced by 1 dose level as outlined in [Table JFCU.9.2](#).

A patient experiencing diarrhea requiring hospitalization (irrespective of grade) or severe diarrhea (Grade 3 or 4) must have dosing suspended (until the toxicity resolves to either baseline or at least Grade 1) and must have the abemaciclib dose reduced by 1 dose level as outlined in [Table JFCU.9.2](#) and [Section 9.3.2.2.1](#).

In the event of Grade 3 or 4 diarrhea, supportive measures may include hydration, loperamide, octreotide, and other antidiarrheals. If diarrhea is severe (that is, requires intravenous hydration) and/or associated with fever or severe (Grade 3 or 4) neutropenia, broad-spectrum antibiotics must be prescribed. Patients with Grade  $\geq 3$  diarrhea or any diarrhea associated with Grade  $\geq 3$  nausea or vomiting should be considered for hospitalization for intravenous hydration and correction of electrolyte imbalance. Events that require a patient to be hospitalized are considered SAEs (see [Section 10.2.1.1](#)).

#### **9.5.4. Antiemetic Therapy**

The use of antiemetic agents is permitted during this study.

##### **9.5.4.1. Analgesic Agents**

The use of analgesic agents is permitted at the discretion of the investigator.

#### **9.5.5. Bisphosphonates and RANK-L Targeted Agents**

Patients with bone metastases present on baseline imaging are allowed treatment with bisphosphonates or RANK-L targeted agents (for example, denosumab), per respective approved labels. Initiation of treatment with bone-modifying agents must begin at least 7 days prior to enrolment. Patients receiving bisphosphonates or RANK-L targeted agents should not switch treatments (for example, replace a bisphosphonate with denosumab) while on study treatment. However, exceptional cases without evidence of PD may be considered in consultation with the Lilly CRP. These exceptional cases will not incur a protocol deviation.

#### **9.5.6. Therapy for Febrile Neutropenia**

Patients experiencing febrile neutropenia, especially with diarrhea or dyspnea, should be managed in a hospital setting according to standard procedures, with the urgent initiation of intravenous antibiotic therapy. Events that require a patient to be hospitalized are considered SAEs (see [Section 10.2.1.1](#)).

### **9.6. Treatment Compliance**

Necitumumab will be administered intravenously at the investigational site, under the direction of the investigator. As a result, a patient's compliance with study drug administration is ensured. Patients should attend scheduled clinic visits and must comply with study criteria under their control.

Compliance with abemaciclib will be assessed at Day 1 and Day 8 of each cycle by evaluating patient diaries and counting returned tablets.

Patients who are significantly noncompliant will be discontinued from the study. A patient will be considered significantly noncompliant if he or she misses more than 5 consecutive days of

study medication, or more than 25% of the intended dose of study medication during any cycle (not applicable in case of omission or dose reduction of abemaciclib due to AE). Similarly, a patient will be considered significantly noncompliant if he or she is judged by the investigator to have intentionally or repeatedly taken  $\geq 125\%$  of the planned doses of study treatment in a cycle.

Potential discontinuation of a patient due to study drug noncompliance will be discussed between the investigator and the Lilly CRP before any determination is made to discontinue the patient.

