- Part A: Dose-escalation part with increasing doses of abemaciclib (100 mg, 150 mg, or 200 mg every 12 hours [Q12H] on Days 1 to 21) to determine a recommended dose range for abemaciclib that may be safely administered in combination with a fixed regimen of necitumumab 800 mg Days 1 and 8 every 21 days in patients with Stage IV NSCLC.
- Part B (expansion cohort): Dose confirmation of abemaciclib in combination with a fixed regimen of necitumumab 800 mg on Days 1 and 8 every 21 days and exploration of clinical antitumor activity.

Approximately 50 patients will be enrolled in Part B: approximately 25 patients with squamous histology and approximately 25 patients with nonsquamous histology.

Patients will be treated until progressive disease, toxicity requiring cessation, protocol noncompliance, or withdrawal of consent. Patients who are on study therapy at study completion may continue to receive study therapy in the extension phase until they meet the discontinuation criteria. Study completion is expected to be approximately 5 months after the last patient has been enrolled.

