#### 7.3.2. *Discontinuation From Study Therapy*

Patients will be discontinued from the study treatment in the following circumstances;

- Enrollment in any other clinical trial involving a study drug or enrollment in any other type of medical research judged not to be scientifically or medically compatible with this study.
- The patient, for any reason, requires treatment with another therapeutic agent that has been demonstrated to be effective for treatment of the study indication; discontinuation from study therapy occurs prior to introduction of the new agent.
- Investigator/Physician Decision
  - The investigator/physician decides that the patient should be withdrawn from the study.
  - If the patient has progressive disease (PD).
- Patient Decision
  - The patient or patient's designee (for example, parents or legal guardian) requests to be withdrawn from the study or study treatment.

- Sponsor Decision
  - The sponsor stops the study or stops the patient's participation in the study for medical, safety, regulatory, or other reasons consistent with applicable laws, regulations, and good clinical practices (GCP).
  - The patient is significantly noncompliant with study procedures and/or treatment.
  - An unacceptable AE/toxicity (for example, a persistent moderate toxicity that is intolerable to the patient).
  - A Grade 3 to 4 infusion-related reaction.

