### **7.3.3. Discontinuation from the Study**

Patients will be discontinued from the study in the following circumstances:

- The investigator decides that the patient should be discontinued from the study.
- The patient or the patient's designee requests that the patient be discontinued from the study.

Patients who are discontinued from study participation will not be followed for PD or survival.

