Provided there is an acceptable safety profile in Part A of this study, Part B will be initiated, which will include a safety interim analysis after the first 15 evaluable patients have completed 2 cycles of study treatment (or otherwise discontinued study treatment). Patients with squamous and nonsquamous NSCLC who received the recommended abemaciclib dose for Part B in Part A will be taken into account for the safety interim analysis.

The final analysis for all outcomes will be performed approximately 5 months after completing enrollment of the study population.

A treatment cycle will be defined as 21 days. Study therapy, consisting of necitumumab plus abemaciclib will continue until there is a radiographic documentation of PD, toxicity requiring cessation, protocol noncompliance, or withdrawal of consent.

Terms used to describe the periods during the study are defined below:

- **Baseline:** begins when the ICF is signed and ends at the first study treatment (or at discontinuation, if no treatment is given).
- **Study Period:** begins at the first study treatment and ends at study completion. The study period does not include the continued access period.
  - **Study Treatment Period:** begins at the first study treatment and ends when the patient and the investigator agree that the patient will no longer continue study treatment. The date of this agreement is to be reported on the case report form (CRF) as the Date of Discontinuation from study treatment.
  - **Postdiscontinuation Follow-Up:** begins the day after the patient and the investigator agree that the patient will no longer continue study treatment.

*Short-term follow-up* begins the day after the patient and the investigator agree that the patient will no longer continue study treatment and lasts approximately 30 days.

[figure not shown]
*Long-term follow-up* begins the day after short-term follow-up is completed and continues until the patient's death or overall study completion.

- **Continued Access Period:** begins after study completion and ends at the end of trial. During the continued access period, patients on study treatment who continue to experience clinical benefit and no undue risks may continue to receive study treatment until one of the criteria for discontinuation is met. The continued access period includes continued access follow-up.

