### **10.1.2. Efficacy Assessments during the Study Period Postdiscontinuation Follow-Up**

Postdiscontinuation follow-up during the study period will be conducted as described in the Study Schedule ([Attachment 1](#)).

For those patients who discontinue study treatment without objectively measured PD, the investigative sites will continue to monitor patients and periodically evaluate tumor response at the same frequency and by the same method used at baseline and throughout the study until the patient has objective disease progression, starts a new anticancer therapy, or until study completion, whichever occurs first. After the patient has objective disease progression or starts a new anticancer therapy, radiologic tests are no longer required and the patient will be followed up approximately every 3 months [ $\pm 7$  days] until the patient's death or overall study completion, whichever comes first.

Response (CR or PR) should be confirmed before the initiation of additional anticancer therapy. However, initiation of new therapy should not be delayed solely to confirm response.

After patients have discontinued study treatment, they may receive additional anticancer therapy at the discretion of the investigator. These postdiscontinuation therapies should be documented on the CRF.

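### Protocol 9.6 takes noncompliant patients off the study, which under 7.3.3 ends PD and survival follow-up, although the rest of the protocol makes noncompliance only a treatment stop

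*Protocol*

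**What the plan says.** Protocol 9.6 defines significant noncompliance as missing more than 5 consecutive days of study medication or more than 25% of the intended dose in any cycle (abemaciclib omissions or reductions due to an adverse event are exempt), or as deliberate or repeated overdosing. The consequence is: "Patients who are significantly noncompliant will be discontinued from the study". A possible discontinuation "will be discussed between the investigator and the Lilly CRP before any determination is made to discontinue the patient".

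Protocol 7.3.3 covers discontinuation from the study. It lists two circumstances, a request by the patient or designee and this one: "The investigator decides that the patient should be discontinued from the study". It then says: "Patients who are discontinued from study participation will not be followed for PD or survival".

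Elsewhere noncompliance ends treatment:
- Synopsis: "Patients will be treated until progressive disease, toxicity requiring cessation, protocol noncompliance, or withdrawal of consent".
- 7.3.2, whose list is of reasons to stop study treatment: "The patient is significantly noncompliant with study procedures and/or treatment".
- 8.1, on study therapy: it "will continue until there is a radiographic documentation of PD, toxicity requiring cessation, protocol noncompliance, or withdrawal of consent".

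After a treatment stop, 10.1.2 applies: "For those patients who discontinue study treatment without objectively measured PD, the investigative sites will continue to monitor patients". Scans run until objective progression, new anticancer therapy or study completion. Attachment 1 sets them at every 6 weeks, with survival contacts every 3 months until death or study completion.

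**The concern.** The protocol separates stopping treatment (7.3.2) from leaving the study (7.3.3) and attaches opposite follow-up to the two. The choice of words in 9.6 therefore decides whether a noncompliant patient is still scanned and contacted. Section 9.6 is also where the thresholds are defined, so a site with a noncompliant patient will look there.

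The primary Part B endpoint is the 3-month PFS rate. Compliance is checked on Days 1 and 8 of each 21-day cycle, so removal can come well before 3 months. A patient removed by then without progression has unknown 3-month status. SAP 5.6.1 censors the patient at the last adequate progression-free assessment. The PFS sensitivity analysis (SAP Table JFCU.5.1) also censors at the last adequate assessment (or first dose, if later), so it does not recover the missing outcome. Survival follow-up ends as well, whenever removal occurs.

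**Working it through.** **1. The texts side by side**

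| Place | What noncompliance ends | Follow-up afterwards |
|---|---|---|
| Synopsis; 7.3.2; 8.1 | study treatment | 10.1.2 and Attachment 1: scans every 6 weeks, survival every 3 months |
| 9.6 read with 7.3.3 | study participation | none for PD or survival |

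Section 9.6 is the outlier. Nothing in it says that follow-up continues.

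**2. The plan's own figures**

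Protocol 12.1 has 50 evaluable patients, a null rate of 50%, an alternative of 65%, and rejection at 60% or more, which is 30 of 50. Exact binomial:
- P(X ≥ 30 | 50, 0.50) = 0.101
- P(X ≥ 30 | 50, 0.65) = 0.814

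These agree with the stated 10% and 81%.

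**3. Illustration of the Kaplan-Meier effect**

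From the documents: 50 patients, null rate 50%, threshold 60% (12.1), scans every 6 weeks (10.1.1), censoring at the last progression-free scan (SAP 5.6.1). Assumed, because the documents give no figures: 2 of 50 removed, so f = 2/50 = 0.04, and a true 3-month rate r of 0.4, 0.3 or 0.2 among those removed. The week-12 scan stands in for 3 months.

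To keep the overall true rate at 0.50, the other 48 patients have rate q = (0.50 − 0.04r)/0.96:
- r = 0.4: 0.484/0.96 = 0.504
- r = 0.3: 0.488/0.96 = 0.508
- r = 0.2: 0.492/0.96 = 0.5125

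*Removed before any post-baseline scan.* Both patients (4% of 50) lose their status and contribute no follow-up. The estimate is the proportion among 48, with mean q. Rejection needs 0.60 × 48 = 28.8, so at least 29.

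*Removed after the week-6 scan.* Assume equal hazard in the two 6-week intervals, so the chance of passing each is √q or √r. The estimate is (progression-free at week 6)/50 times the proportion of those still followed who pass the second interval. For r = 0.4 the week-6 expectation is (2 × 0.632 + 48 × 0.710)/50 = 0.707, and 0.707 × 0.710 = 0.502. A removed patient who had already progressed by week 6 keeps a known status. Those who lose it number 2√r, or 0.9 to 1.3 patients, which is 1.8-2.5% of 50. Rejection probabilities come from exact enumeration.

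| r | Before any scan: mean estimate | False rejection | After week 6: mean estimate | False rejection |
|---|---|---|---|---|
| 0.5 (no bias) | 50.0% | 0.097 | 50.0% | 0.076 |
| 0.4 | 50.4% | 0.107 | 50.2% | 0.080 |
| 0.3 | 50.8% | 0.118 | 50.4% | 0.084 |
| 0.2 | 51.3% | 0.130 | 50.5% | 0.088 |

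The no-bias row differs from 0.101 only because censoring changes the attainable values of the estimate, so each column should be read against its own first row. The excess is 0.010-0.033 before any scan and 0.004-0.012 after week 6.

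**The case against.** The strongest reply is that the protocol shows what was meant. Section 7.3.2 names noncompliance as a treatment stop and places it under sponsor decision. The same list speaks loosely of withdrawing a patient from the study when the consequence is stopping treatment. The two circumstances in 7.3.3 do not include noncompliance. Section 7.3 sends all discontinued patients to the Study Schedule. And 9.6 requires a discussion with the sponsor's physician before anyone is removed.

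Most of this stands as evidence of intent, and it makes a literal misreading less likely. It does not remove the conflict. The sentence in 9.6 is mandatory and says study. Section 7.3.3 includes an investigator's decision to discontinue a patient from the study, and its sentence on follow-up is more specific than the general one in 7.3. The required discussion is a chance to catch the misreading, but 9.6 does not say whether its subject is treatment or study.

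The reply is also right that few patients may be exposed. Adverse-event omissions and reductions of abemaciclib are exempt, and 9.3.1 tolerates supply interruptions of up to 5 days, or longer by agreement. The loss scales with the number removed and is zero if nobody is.

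**Conclusion.** The inconsistency is real. Applied literally, 9.6 with 7.3.3 stops assessments that the rest of the protocol requires. OS data are lost for any such patient still alive, and 3-month PFS status is lost for those removed before 3 months without progression. Kaplan-Meier bias is upward if removal goes with poor prognosis and absent if removal is unrelated to it. With 2 of 50 removed and the assumed rates, it is at most 1.3 percentage points.

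The documents do not support two stronger readings:
- *The trial's type I error is seriously inflated.* Assuming 5 of 50 removed, all before any post-baseline scan, false rejection is 0.15-0.23 against a no-bias 0.116. That is an extreme corner, and no document gives a removal rate. The stated alpha and power are correct for the design.
- *The trial loses substantial power.* Counting removed patients as failures under the 30-of-50 rule would lower power from 0.81 to 0.75-0.79 with 2 removed, under the same assumed rates. No document says that unknown status counts as failure, and the planned estimate is Kaplan-Meier.

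Protocol 8.2 describes the outcome as hypothesis generating only. The case for a change is avoidable loss of primary-endpoint and survival data at almost no cost to prevent.

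**What to change.** In Protocol 9.6, replace the words that take the patient off the study with *discontinued from study treatment (Section 7.3.2)*. Add one sentence stating that tumor assessments and survival follow-up continue per Section 10.1.2 and Attachment 1.

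The cost is one phrase and one sentence. Sample size, decision rule, alpha, power and visit schedule are unchanged, and the extra scans and contacts use the schedule already in place for other treatment stops. Recovery will be partial: scans still end at new anticancer therapy, and some noncompliant patients may miss them.
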